## 9.4 Study Endpoints

### 9.4.1 Primary

Sextant based analyses using prostatectomy whole-mount analysis or biopsy as Gold Standard (Appendix D):

- Sensitivity, specificity, Receiver operator curve (ROC) of mpMRI overall and for each Gleason pattern (3, 4, 5)
- Sensitivity, specificity, ROC of PSMA PET-CT overall and for each Gleason pattern (3, 4, 5)

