## 3 BACKGROUND

### 3.1 Background & Preliminary Work

Up to 60% of men in the U.S. unwittingly have Gleason 6 (pure pattern 3: 3+3) prostate cancer by their 80s on autopsy, which argues for active surveillance of this tumor (Zlotta, et al. 2013). Long-term active surveillance cohorts demonstrate low (<5%) 15-year metastasis rates (Musunuru, et al. 2017). However, <50% choose active surveillance when diagnosed on biopsy with Gleason 6 prostate cancer (Womble, et al. 2015). This is due to multiple factors: (1) prostate cancer is multi-focal in >80%; (2) prostate cancer commonly has mixed grade lesions; and (3) conventional imaging modalities (US, MRI) miss significant cancer. There is also disagreement on what follow-up is needed during active surveillance. Molecular imaging agents would bring assurance and peace of mind to hundreds of thousands of men, if they are capable of selectively detecting clinically significant prostate cancer (Gleason patterns 4 and 5). *We expect to determine whether the PSMA-targeted PET agent, Ga-PSMA-11, reliably detects significant prostate cancer and what minimum percentage Gleason pattern 4 is required for detection by comparison of PET/MR to whole mount analysis.*

Multiparametric 3-T MRI has shown the ability to locate prostate cancer lesions that are higher grade and increased size. For example, MRI-targeted biopsy increases the detection of clinically significant prostate cancer using fewer cores than template biopsy (Pokorny, et al. 2017, Wysock, et al. 2014), while reducing detection of insignificant Gleason 6. However, recent studies mapping MRI lesions to final whole-mount pathology show limitations. For example, a recent study showed only 80% of index (largest) tumors were seen by MRI and even fewer clinically significant non-index lesions (Le, et al. 2014). Another recent study showed MRI missed a clinically significant lesion in 26% of patients using whole-mount analysis (Borofsky, et al. 2017). Fittingly, Borofsky titled their paper, “What are we missing? False negative cancers at Multiparametric MR imaging of the prostate.” MRI interpretation has also been shown to vary substantially across radiologists, which persisted after correcting for radiologist practice volume (Son, et al. 2017). Therefore, the majority of urologists still take ultrasound-based template biopsies at the time of MRI guided biopsy (MRI-ultrasound fusion).

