#### **7.3.4 Surgery and Pathology**

- The standard of care surgical procedure is performed as indicated by the cancer.
- Pathologic assessment: whole mount sections of prostate tissue and routine sections of lymph nodes if applicable will be fixed and analyzed by licensed pathologist per routine care. This typically happens within 2 weeks of prostatectomy.
- Additional study-related pathologic assessment: intraprostatic lesion-based assessment will be done to document the % Gleason pattern 3, 4, and 5 within each lesion.
- A sextant-based analysis will be performed. See appendix D for details of sextant analysis.
- A secondary “per lesion” analysis will also be performed.
- How the knowledge of the PSMA-PET informs treatment will be tracked. Examples of informing the decision include the number and location of Ga-PSMA-PET detected: additional intraprostatic cancer lesions diagnosed, extra-prostatic extension, seminal vesicle invasion, and lymph node invasion.
- Genomic studies (e.g. Decipher, mRNA sequencing, or similar) may be done as standard of care for medical management following biopsy or surgery or may be done for determining association of mRNA (e.g. FOLH1 or others) and imaging characteristics.

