### 9.3 Sample Size

Table 1: Sample size calculation:

	sensitivity= 0.80	sensitivity= 0.85	sensitivity= 0.90	sensitivity= 0.95
Error allowed (d)= 7.5%	46	37	27	14
Error allowed (d)= 10%	27	21	15	8

Our sample size is based on the key primary endpoint of sensitivity to detect clinically significant (Gleason >6 and >5mm) cancer overall. In the Table above we summarized the sample size required to achieve a certain degree of accuracy for different sensitivity levels. All the calculations are based on the normal approximation of the binomial distribution. For this pilot, we will also assume the samples within each patient are independent statistically. Each patient has six samples for diagnostic testing (sextants) and the prevalence of cancer per sextant is estimated to be 40% (Eiber et al., 2016). The rows (d) present the marginal maximal error under 95% confidence interval and the columns represent the sensitivity rate. The numbers in Table 1 represent the required number of patients needed for each different combination of marginal error (d) and sensitivity rate. In other words, for a sensitivity of 90% and a marginal error of 7.5%, we

are 95% sure that the sensitivity lies between 82.5% and 97.5% if we enroll 27 patients. Based on Table 1, the maximal sample size is 46 assuming the sensitivity is 80%. Therefore, we decided 36 patients was adequate to ensure that the proposed trial can achieve certain accuracy of the sensitivity across the majority the scenarios considered in Table 1.

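### Per-pattern accuracy is a primary endpoint, but positive and negative sextants are not defined for each Gleason pattern, so pattern-5 specificity and pattern-3 sensitivity could mislead

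*Combined protocol and SAP*

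**What the plan says.** Section 9.4.1 sets the primary endpoints by sextant, with whole-mount pathology or biopsy as reference: "Sensitivity, specificity, Receiver operator curve (ROC) of mpMRI overall and for each Gleason pattern (3, 4, 5") and "Sensitivity, specificity, ROC of PSMA PET-CT overall and for each Gleason pattern (3, 4, 5"). The synopsis lists the same measures by pattern but leaves out the overall analysis, so there the per-pattern measures are the only primary outcomes.

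Section 9.7 estimates sensitivity and specificity by GEE. It draws ROC curves over SUV for PET and over suspicion score for mpMRI, picks a threshold by the Youden index, and compares the modalities by McNemar test. Appendix D names the six sextants and adds that 3+3 disease and lesions under 5 mm are generally not clinically relevant. None of these places says which sextants are positive or negative for pattern 3, 4 or 5, or how a sextant holding more than one pattern is classed.

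Three other places bear on the point:

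- Section 3.1 gives the scientific aim, an agent "capable of selectively detecting clinically significant prostate cancer (Gleason patterns 4 and 5"), and notes that mixed-grade lesions are common.
- Section 7.3.4 has the pathologist "document the % Gleason pattern 3, 4, and 5 within each lesion".
- Section 9.3 says: "Our sample size is based on the key primary endpoint of sensitivity to detect clinically significant (Gleason >6 and >5mm) cancer overall".

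**The concern.** SUV and suspicion score each say how suspicious a sextant is. Neither says which Gleason pattern it holds. Turning one such score into three sensitivities, three specificities and three ROC curves depends wholly on how sextants are assigned to the positive and negative class for each pattern, and the plan leaves that open.

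Two results are at risk:

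- **Pattern-5 specificity.** In the ordinary sense of specificity, a sextant without pattern 5 is a pattern-5 negative. A correct call on 3+4 or 4+3 cancer there is then scored as an error.
- **Pattern-3 sensitivity.** A 3+4 sextant contains pattern 3. A tracer that sees only pattern 4 is therefore credited with detecting pattern 3, and a reader may conclude that it picks up indolent disease when it does not.

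Both results sit among the primary endpoints. If the class definitions are settled after the data are seen, the choice alone can move a primary result by tens of percentage points.

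**Working it through.** **The plan's own figure.** The documents give no figure for per-pattern accuracy. The only related calculation is the table in section 9.3. Its inputs are "Each patient has six samples for diagnostic testing (sextants) and the prevalence of cancer per sextant is estimated to be 40" per cent, "The rows (d) present the marginal maximal error under 95% confidence interval and the columns represent the sensitivity rate", and "All the calculations are based on the normal approximation of the binomial distribution". The formula is patients = 1.96² × p(1 − p) / d² / (6 × 0.40), rounded up. For p = 0.80 and d = 0.075 this is 109.27 / 2.4 = 45.53, so 46, as stated. The full table comes out as 46, 37, 26, 14 and 26, 21, 15, 8, against the stated 46, 37, 27, 14 and 27, 21, 15, 8. The two cells stated as 27 follow with z = 2. The sizing uses overall sensitivity only, so the per-pattern question does not touch it.

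**Inputs for the check.**

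- From section 9.3: 40% of sextants have cancer. With 36 patients there are 216 sextants.
- Assumed, because the documents do not split the 40% by pattern: 35% pure pattern 3, 60% with pattern 4 but no 5, 5% with pattern 5. As shares of all sextants: benign 0.60, pure 3 0.14, any 4 without 5 0.24, any 5 0.02.
- Also assumed: sextants with 4 but no 5 contain some pattern 3, and sextants with 5 contain pattern 4 but not 3.

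**A perfect detector of patterns 4 and 5 (flags 0.26 of sextants), negatives = all sextants lacking the pattern.**

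1. Pattern-5 specificity = (0.60 + 0.14) / 0.98 = 0.755. In counts, 0.24 × 216 = 51.8 correctly found cancer sextants are scored as false positives.
2. Pattern-4 specificity = (0.60 + 0.14) / 0.74 = 1.00, so there is no distortion.
3. Pattern-3 sensitivity = 0.24 / (0.14 + 0.24) = 0.632, although no pure pattern-3 sextant is flagged.

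**Varying the pure-3 share, with the pattern-5 share held at 5% of cancer sextants.**

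- 20%: pattern-5 specificity 0.68 / 0.98 = 0.694; pattern-3 sensitivity 0.30 / 0.38 = 0.789.
- 50%: pattern-5 specificity 0.80 / 0.98 = 0.816; pattern-3 sensitivity 0.18 / 0.38 = 0.474.

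**Varying the rest.** With c the share of sextants holding pattern 4 or 5 and q the share holding 5, pattern-5 specificity is (1 − c) / (1 − q). For c from 0.15 to 0.30 and q from 0.01 to 0.05 it runs from 0.71 to 0.90. If sextants with pattern 5 also hold pattern 3, pattern-3 sensitivity is (0.24 + 0.02) / 0.40 = 0.65.

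**Negatives = benign sextants only.**

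- The perfect 4/5 detector has specificity 0.60 / 0.60 = 1.00 for every pattern, so the pattern-5 loss disappears.
- Pattern-3 sensitivity does not involve the negatives and stays at 0.632.
- A tracer that also flags every pure pattern-3 sextant still has pattern-4 specificity 0.60 / 0.60 = 1.00. With all sextants lacking pattern 4 as negatives, it would score 0.60 / 0.74 = 0.81. Benign-only negatives therefore hide the lack of selectivity that section 3.1 asks about.

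**An imperfect test, for the PET–MRI comparison.** Assume specificity 0.90 in benign sextants and detection of 0.40 in pure 3, 0.85 in any 4 without 5, and 0.95 in any 5. With all sextants lacking the pattern as negatives:

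- Pattern-5 specificity = (0.60 × 0.90 + 0.14 × 0.60 + 0.24 × 0.15) / 0.98 = 0.660 / 0.98 = 0.673.
- Pattern-3 sensitivity = (0.14 × 0.40 + 0.24 × 0.85) / 0.38 = 0.684, against 0.40 in pure pattern 3.
- If pattern-4 detection falls from 0.85 to 0.65, pattern-5 specificity rises to (0.54 + 0.084 + 0.084) / 0.98 = 0.722. The worse detector looks more specific.

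**The case against.** A reader might infer that the plan counts correctly detected cancers of another pattern as false positives, and that even a perfect test would therefore look non-specific. The documents do not support that. No section states the negative class, and with benign-only negatives the specificity loss vanishes. It is not general even on the literal reading: a perfect 4/5 detector scores 1.00 for pattern 4. Counting uptake in pure pattern 3 as false there matches the aim in section 3.1.

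A reader might also infer a separate Youden cut-off for each pattern. Section 9.7 speaks of one optimal threshold and does not say that it is set by pattern.

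Further points on the other side are fair:

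- The pattern split and detection rates are assumed.
- The specificity problem falls mainly on pattern 5, which in the assumed split is 0.02 × 216, about 4 sextants. Eligibility centres on grade groups 1 to 3, with Gleason 8 or 9 lesions allowed only in addition. Any pattern-5 result would be descriptive.
- Section 9.3 already names clinically significant cancer overall as the key endpoint, and section 9.4.2 looks at percentage of pattern 4 within 3+4 disease.
- Section 9.7 calls the pilot data hypothesis generating.

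All of this stands, and it limits the point. It does not reduce it to a missing definition that any choice would repair. Benign-only negatives leave pattern-3 sensitivity driven by mixed sextants and stop pattern-4 specificity from testing selectivity. The literal choice distorts pattern 5.

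**Conclusion.** The point holds in a limited form. The per-pattern primary endpoints lack a rule for positive, negative and mixed sextants, and neither obvious rule for the negatives makes all three patterns interpretable.

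- If all sextants lacking the pattern are negatives, a perfect 4/5 detector reports pattern-5 specificity of about 0.76 (0.69 to 0.82).
- Under either choice it reports pattern-3 sensitivity of about 0.63 (0.47 to 0.79), although it detects no pure pattern 3.
- If only benign sextants are negatives, specificity is not lost, but pattern-4 specificity says nothing about uptake in pure pattern 3.

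The 40% prevalence is the plan's. The split by pattern, and which patterns occur together in a sextant, are assumptions; other splits change the size, not the direction. Pattern-4 specificity on the literal reading, the overall analysis and the sample size are sound on this point. This is a worthwhile, cheap improvement to make before the data are analysed. It does not invalidate the trial.

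**What to change.** In the synopsis and in sections 9.4.1, 9.7 and Appendix D:

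1. Class each sextant once by its highest pattern: benign, pure 3, any 4 without 5, any 5. State whether the size limit in section 9.3 applies and where smaller lesions go.
2. Report the detection rate in each class, for PET and for mpMRI.
3. Report specificity from sextants without clinically significant cancer, with a benign-only version alongside.
4. Fit the main ROC curve and Youden cut-off to the cumulative target (any pattern 4 or 5), in line with the key endpoint in section 9.3.
5. Include the overall analysis in the synopsis.

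The cost is wording. The pattern percentages are already recorded by lesion at surgery (section 7.3.4). For biopsy patients, the class would come from the pathology that the sextant analysis already needs. The downside is that separate specificities and ROC curves for patterns 3 and 5, now listed as primary outputs, are dropped or become descriptive only. If the sponsor wishes to keep them, the minimum is to state the positive and negative sextants for each pattern and the handling of mixed sextants, and to report detection in pure pattern-3 sextants on its own.

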### 9.4.2 Secondary

- Lesion based analysis of accuracy
- For 3+4: Sensitivity and specificity of mpMRI based on Gleason %pattern 4
- For 3+4: Sensitivity and specificity of PET-CT based on Gleason %pattern 4
- Sensitivity and specificity for extra-capsular extension (mpMRI vs PET-CT)
- Sensitivity and specificity for seminal vesicle invasion (mpMRI vs PET-CT)
- Impact of PSMA PET-CT on treatment plan for surgery:
  - Additional lesions found, Additional sextants involved, extra-capsular extension detected, seminal vesicle invasion detected, lymph node invasion detected.
- Impact of PSMA PET-CT on treatment plan for biopsy:
  - Additional lesions found, Additional sextants involved

## 9.5 Participant Characteristics

Demographic characteristics will be summarized using descriptive statistics.

## 9.6 Concomitant Medications

Concomitant medications will be coded using the WHO Drug dictionary and will be summarized in tabular format.

## **9.7 Analysis of Primary Objective**

We will use the generalized estimation equation (GEE) to fit the data and estimate the sensitivity and specificity. We will use the receiver operating characteristic (ROC) curve to represent the values of sensitivity and specificity at different thresholds (PET= SUV, mpMRI=suspicion scores). According to the ROC curve, we will determine the optimal threshold with a minimal sensitivity of 50% by maximizing the Youden index. We will use the McNemar test to compare the sensitivity and specificity values between PET and MRI although data from this pilot study is considered hypothesis generating only due to the small sample size. In addition, we will use the bootstrapping method to detect the significant difference of the area under curve (AUC) with different ROC curves.

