## PROTOCOL SYNOPSIS

Primary Objectives:	Define the accuracy of $^{68}\text{Ga}$ -PSMA-11 PET-CT for detecting the location and size of clinically significant prostate cancer lesions in low and intermediate risk disease.
Secondary Objectives:	Evaluate how knowledge of the PSMA-PET might inform treatment planning.
Exploratory Objectives:	Generate pilot data to be validated in larger studies
Study Design:	Prospective, early phase clinical trial, single arm
Test Factor/Exposure:	Intravenous injection of $^{68}\text{Ga}$ -PSMA-11 and detection with PET-CT scanner
Duration of Treatment:	Patients will undergo injection of $^{68}\text{Ga}$ -PSMA-11 PET-CT and pre-treatment MRI scan and followed until biopsy and/or surgical resection.
Enrollment:	Subject accrual is planned for 24 months
Inclusion Criteria:	
 
1. <math>\geq 18</math> years of age
 
2. Must provide written informed consent
 
3. Presence of low or intermediate risk prostate cancer or at risk of having intermediate risk cancer 
 
a. Intermediate risk prostate cancer: 
 
i. Grade group 2 = 3 + 4, or
 
ii. Grade group 3 = 4 + 3
 
 
 
b. At Risk of intermediate risk prostate cancer: 
 
i. 4K score <math>\geq 20\%</math>, or
 
ii. Select MDx <math>\geq 20\%</math>, or
 
iii. PSA Density <math>\geq 0.15</math>
 
iv. Grade group 1 = 3+3
 
 
 
 
 
4. Scheduled for MRI or has recently completed SOC MRI (within 6 months) for further biopsy, surgical removal or focal therapy.
 
5. Willing and able to lie still for approximately 50 minutes in an enclosed space for the CT
 

[figure not shown]
Exclusion Criteria:	
 
1. Participation in another investigational trial involving research exposure to ionizing radiation concurrently or within 30 days.
 
2. Does not meet safety criteria for MRI scan (e.g. metal implant that is not allowed).
 
3. Significant acute or chronic medical, neurologic, or illness in the subject that, in the judgment of the Principal Investigator, could compromise subject safety, limit the ability to complete the study, and/or compromise the objectives of the study.
 

Number of Subjects:	36 patients

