## **9.8 Analysis of Secondary Objectives**

The proportion of patients who had cancer detected by both the standard of care imaging (MRI) and the Ga-PSMA-11 PET imaging will be calculated, along with exact 95% confidence intervals. A similar approach will be used for other secondary outcomes in Section 9.4.2 to compare the cancer detection of the mpMRI and Ga-PSMA-11 detection method to the surgical observations and the clinical tissue histopathology findings.

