### **Fusion Biopsy Procedure**

Concurrent acquisition of  $^{68}\text{Ga}$ -PSMA-11 PET data will be added to our present standard-of-care prostate mpMRI protocol performed in support of surgery planning or fusion biopsy for patients with prostate cancer. There are commercially available devices which allow performing a biopsy by **fusing** the MR targeted lesion with the real-time trans-rectal ultrasound image and thereby increasing the chance of prostate cancer detection. The fusion biopsy will be performed in the urology clinic, with at least two cores from each regions-of-interest defined by both mpMRI and PET.

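### Section 9.7 tunes each cut-off on the trial's own data without saying which cut the accuracy estimates use; at the tuned cut they would be optimistic and uncorrected

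*Combined protocol and SAP*

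**What the plan says.** Section 9.7 is the whole primary analysis plan. It estimates sensitivity and specificity by GEE, draws ROC curves over SUV for PET and over suspicion scores for mpMRI, and then states "we will determine the optimal threshold with a minimal sensitivity of 50% by maximizing the Youden index". McNemar's test compares PET with MRI. Neither the GEE sentence nor the McNemar sentence names a cut-off, and no SUV or suspicion-score cut-off is fixed in advance anywhere in the documents.

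The only resampling is for the ROC areas: "we will use the bootstrapping method to detect the significant difference of the area under curve (AUC) with different ROC curves". No split sample, cross-validation or optimism correction is described. Section 9.7 adds that "data from this pilot study is considered hypothesis generating only due to the small sample size", and the synopsis lists as the exploratory objective "Generate pilot data to be validated in larger studies".

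Other sections imply that some positive imaging calls will exist:

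- Section 7.3.2 has readers mark suspicious lesions while blinded.
- Section 9.4.2 counts "Additional lesions found, Additional sextants involved".
- Section 9.8 counts patients whose cancer both modalities detected.
- Appendix C plans fusion biopsy "with at least two cores from each regions-of-interest defined by both mpMRI and PET".

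None of these is tied to the sextant sensitivity and specificity of section 9.7. Appendix D names the six sextants and refers the method to a cited study, but gives no rule for calling a sextant positive.

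**The concern.** GEE and McNemar both need a yes/no imaging call for each sextant. The Youden cut is the only operating point in section 9.7, so an analyst could reasonably use it. Another could use the readers' marks and report a different primary sensitivity from the same data.

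If the Youden cut is used, the cut that looks best in these sextants is then judged on them, and part of its apparent advantage is chance. Sensitivity is the quantity on which section 9.3 sizes the trial, and it would be reported too high on average. A continuous SUV offers many more candidate cuts than a short ordinal score and so gains more from the search, which can tilt the comparison toward PET. These values are also meant to support later, larger trials (section 4.3 and the synopsis), so the excess would carry into their planning.

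**Working it through.** **Inputs from the protocol.** Section 9.3 gives 36 patients, six sextants each and 40% of sextants with cancer: 36 × 6 = 216 sextants, 216 × 0.40 = 86.4 positive and 129.6 negative. Section 3.1 quotes AUCs of 0.73 (MRI) and 0.88 (PET) from a retrospective study. Section 9.7 gives the cut-off rule.

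**Step 1: the plan's own precision.** Section 9.3 uses patients = 1.96² × p(1 − p) / d² / (6 × 0.40).

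- p = 0.80, d = 7.5%: 3.8416 × 0.16 / 0.005625 = 109.27 positive sextants; 109.27 / 2.4 = 45.53, rounded up to 46, as in the plan's table.
- All eight cells agree to within one patient. Two come out at 26 where the table has 27.
- At 36 patients the half-width is 1.96 × √(p(1 − p) / 86.4): 8.4, 7.5, 6.3 and 4.6 points for sensitivity 0.80, 0.85, 0.90 and 0.95.

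**Step 2: simulation of the rule.** Scores were binormal, with within-patient correlation 0 or 0.3. The cut was the one maximising sensitivity + specificity − 1 subject to sensitivity of at least 0.50. Optimism is the apparent accuracy minus the true accuracy at the chosen cut, averaged over 6,000 runs per setting. The assumptions are the score model, the AUC range, the correlation, five MRI levels in two layouts, and an SUV floor exceeded by 20% of negative sextants. The table shows 40% prevalence, correlation 0, with the cut midway between adjacent scores. Each cell is the overstatement of sensitivity, then specificity, in points.

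| AUC | SUV in every sextant | SUV above a floor | Five-level MRI score (two layouts) |
|---|---|---|---|
| 0.73 | 3.5, 2.2 | not used | 1.6, 0.7 or 0.5, 0.3 |
| 0.80 | 3.1, 2.0 | 1.7, 0.9 | 1.4, 0.9 or 1.5, 0.8 |
| 0.88 | 2.7, 1.8 | 2.0, 1.2 | 1.2, 1.0 or 0.7, 0.5 |

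The floor was not used at AUC 0.73 because the 50% sensitivity limit often binds there. Over both correlations and both ways of placing the cut, the ranges are 2.7–3.8 and 1.6–2.5 points with SUV in every sextant, 1.7–2.3 and 0.7–1.3 with a floor, and 0.5–1.6 and 0.3–1.1 for the MRI score. A separately written simulation (4,000 runs) gave 3.0–3.7 and 1.7–2.0 for a continuous score, and 1.3–1.7 and 0.8–1.1 for a five-level one.

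**Step 3: against the planned margin.** For PET sensitivity, 1.7 / 10 = 17% and 3.8 / 7.5 = 51%.

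**Step 4: tilt between modalities**, in sensitivity plus specificity. At AUC 0.88 for both: (2.7 + 1.8) − (1.2 + 1.0) = 2.3 points, or 4.5 − (0.7 + 0.5) = 3.3 with the other layout. Over all settings, including PET 0.88 against MRI 0.73, the tilt is 2.2–5.0 points, or 0.2–2.4 with a floor.

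**Step 5: fewer positive sextants.** Section 9.4.1 also makes accuracy for each Gleason pattern primary, and some patterns may be rare. The prevalences here are assumed. At 20%, PET sensitivity is overstated by 4.7–6.0 points (3.5–3.7 with a floor). At 5% there are 216 × 0.05 = 10.8 positive sextants, and at AUC 0.80 the apparent value is 0.820 against a true 0.681, an excess of 13.9 points. The range at 5% is 12–15 points (10–12 with a floor), but the 95% interval there is already about ±25 points.

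**Step 6: does holding out a patient remove it?** Sensitivity with correlation 0.3, 1,200 runs:

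| Setting | Apparent | True | Leave-one-patient-out |
|---|---|---|---|
| 40%, AUC 0.80 | 0.745 | 0.712 | 0.709 |
| 40%, AUC 0.88, floor | 0.770 | 0.749 | 0.745 |
| 20%, AUC 0.80 | 0.761 | 0.709 | 0.699 |
| 5%, AUC 0.80 | 0.823 | 0.685 | 0.679 |

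The held-out estimate lies within 1.0 point of the truth in each row.

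**Step 7: interval coverage** (nominal 95%; two sets of 400 runs, 40%, AUC 0.80, correlation 0.3).

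- GEE at the tuned cut: 91.8% and 94.8%.
- GEE at a fixed cut: 94.2% and 95.0%.
- GEE on held-out calls: 90.2% and 91.2%.
- Patient bootstrap of the held-out estimate, standard error on the logit scale: 94.0% and 96.0%.

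Coverage at the tuned cut depends on how the interval is built: a plain Wald interval covered 87–88% at 40% with independent sextants.

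**The case against.** The bias is conditional. Section 9.7 lists the GEE estimates, the Youden cut and McNemar's test without linking them, so the cut may be only a descriptive output. If the blinded reader marks define positivity, or if the study cited in Appendix D supplies a rule, no tuning bias arises. This stands, and it is why the point is put as an if. It also confirms that the operating point is unstated.

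The effect is modest. At the only prevalence in the documents it is below the planned margin, and it is smaller still if SUV exists only for marked lesions. That stands too. The large figure at 5% prevalence rests on an assumption and sits inside a very wide interval. No error rate for McNemar's test was computed, so the effect of the tilt on that test is not known.

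The trial calls itself hypothesis-generating and leaves validation to later studies. This limits the consequence, since no decision rule depends on the value. But the caveat concerns small numbers, that is, imprecision, and does not offset an error in one direction. Later validation does not correct what this trial reports.

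The full correction is elaborate for a pilot, and at 5% prevalence the bootstrap intervals tested covered only 84–87%. That is fair: the bootstrap interval matters less than naming the cut and giving a held-out point estimate.

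**Conclusion.** The concern holds. It is certain from the text that section 9.7 tunes its cut-offs on the trial's own data, does not say which cut GEE and McNemar use, and plans no correction for tuning. If the tuned cut is used, the direction of the bias does not depend on the simulation's details.

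Its size does depend on them. At 40% prevalence it is about 2 to 4 points in PET sensitivity and 1 to 2.5 in PET specificity, with less for MRI. With few positive sextants it is larger. These figures rest on the assumptions listed in step 2 and on the assumed lower prevalences. The AUC comparison is unaffected. The plan should be changed on this point, but the issue does not threaten the trial.

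**What to change.** 1. **Name the operating point.** State in section 9.7 which calls the GEE estimates and McNemar's test use. Where blinded reads can be mapped to sextants, report accuracy at those calls, fixed before outcome data are examined. This removes the tuning bias.
2. **If the Youden cut is used,** label the in-sample values as apparent and add a leave-one-patient-out estimate: choose the cut from the other 35 patients, apply it to the held-out patient's six sextants, and pool over patients.
3. **For that estimate's interval,** resample whole patients, repeat the cut selection in each resample with all copies of a patient left out together, and use the bootstrap standard error on the logit scale. Do not rely on the ordinary GEE interval for held-out calls, and treat McNemar's test on them as descriptive.
4. **For a Gleason pattern with few positive sextants,** give counts and accuracy at fixed calls only.

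The cost is a few sentences and a short program (36 refits per modality for the point estimate), with no new scans or tissue. Reported PET sensitivity would fall by about 2 to 4 points. With SUV in every sextant, its interval would be about 30–45% wider than the naive one. The reader-call route needs confirmation that marks are, or can be, recorded by sextant.

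### Section 9.7 does not say which ROC sets the cut-off; run on each pattern's own ROC, the rule holds pattern-3 sensitivity at 50% or more and makes sensitivities non-comparable across patterns

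*Combined protocol and SAP*

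**What the plan says.** Section 9.4.1 lists as primary, on a sextant basis, "Sensitivity, specificity, ROC of PSMA PET-CT overall and for each Gleason pattern (3, 4, 5"), with a matching item for mpMRI. The synopsis also lists the per-pattern results as primary.

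Section 9.7 builds the ROC over "different thresholds (PET= SUV, mpMRI=suspicion scores") and then states: "we will determine the optimal threshold with a minimal sensitivity of 50% by maximizing the Youden index". This is the only rule in the plan that turns a ROC into a cut-off. Its wording is singular ("According to the ROC curve, we will determine the optimal threshold"). It does not say whether there is one cut-off per modality or one per pattern, which target defines the positives, or which sextants are the negatives for a pattern-specific ROC.

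Two other places bear on the reading. Section 3.1 says the value of such agents depends on whether they are "capable of selectively detecting clinically significant prostate cancer (Gleason patterns 4 and 5"). Section 9.3 sizes the trial on the "key primary endpoint of sensitivity to detect clinically significant (Gleason >6 and >5mm) cancer overall".

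**The concern.** Selectivity for patterns 4 and 5 means low detection of pattern 3. The most direct display of that is a low pattern-3 sensitivity beside a high pattern-4 sensitivity at the same cut-off. Reading 9.4.1 and 9.7 together, an analyst could reasonably draw three ROCs per modality and apply the rule to each. Two things then go wrong:

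- On the pattern-3 ROC, only cut-offs that call at least half of the pattern-3 sextants positive are admissible. A low pattern-3 sensitivity cannot be reported.
- Each pattern has its own SUV cut-off. The same sextant SUV can be positive for pattern 3 and negative for pattern 4, so the three sensitivities do not describe one test.

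An analyst who sets one cut-off and applies it throughout would report very different pattern-3 figures from the same data. The plan leaves that choice open until the data are in hand, for a named primary outcome.

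**Working it through.** **The plan's own figures.** The 50% floor is a rule with no figure to reproduce. The related calculation is Table 1 in 9.3: patients = 1.96² × p(1 − p) / d² / (6 × 0.40), rounded up. It gives 46, 37, 26, 14 (d = 7.5%) and 26, 21, 15, 8 (d = 10%), matching the plan except for two cells of 26 against a stated 27. Table 1 concerns significant cancer overall, not a contrast between patterns.

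**Step 1, by definition.** Let the rule choose c to maximise Se(c) + Sp(c) − 1 over cut-offs with Se(c) ≥ 0.50. On whichever curve it is run, the reported sensitivity is at least 0.50. On the pattern-3 curve, pattern-3 sensitivity is therefore at least 50%. No assumption about the scan is needed.

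**Step 2, size on normal scores.** Assumed, not in the documents: 30 pattern-3-only, 100 benign and 60 significant sextants, independent, with significant-cancer AUC 0.88. The pattern-3 ROC is against benign sextants; for the common cut-off, pattern-3-only sextants count as negatives. Mean pattern-3 sensitivity:

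| Pattern-3 AUC | Own cut-off, with floor | Own cut-off, no floor | One cut-off set on significant cancer |
|---|---|---|---|
| 0.50 | 79% (specificity about 32%) | 61% | 19% |
| 0.60 | 72% | 64% | 28–29% |
| 0.70 | 72% | 71% | 41% |

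Hand check of the last column at AUC 0.50: AUC 0.88 gives a separation of √2 × Φ⁻¹(0.88) = 1.66. The Youden cut-off against benign is half of that, 0.83, and a pattern with benign uptake exceeds it with probability 1 − Φ(0.83) = 20%.

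**Step 3, splitting the gap.** At AUC 0.50 the gap is 79 − 19 = 60 points: 79 − 61 = 18 from the floor and 61 − 19 = 42 from using a separate cut-off. At AUC 0.70 the floor adds only about 2 points before rounding; the rest of the gap of about 31 comes from the separate cut-offs.

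**Step 4, a second model.** Lognormal SUVs were matched to section 3.1 (lesions median 10.6, IQR 8–14; benign 3.8, IQR 3–5). Sextants: 36 × 6 = 216, with 40% positive giving about 86, split by assumption into 30 pattern-3-only and 56 pattern-4/5, plus 130 negative. Over 2,000 runs with pattern-3 uptake equal to benign:

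- Separate cut-offs: pattern 3 has sensitivity 79%, specificity 31% and Youden 0.11 at SUV about 3.0. Pattern 4/5 has 92%, 92% and 0.83 at SUV about 6.4.
- One cut-off from the pattern-4/5 ROC: pattern-3 sensitivity is 8%. It is 23% and 53% if the pattern-3 median SUV is 5 or 7.
- One cut-off from the overall-cancer ROC: 13%, 41% and 72% for pattern-3 medians of 3.8, 5 and 7.
- AUC: 0.50 for pattern 3 against 0.97 for pattern 4/5. The pattern-4/5 AUC was the higher in 100%, 100% and 93% of runs across those three medians.
- On the pattern-4/5 ROC the unconstrained Youden cut-off always had sensitivity of at least 50%, so the floor had no effect there.

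**The case against.** The strongest reply is that 9.7 is singular and never tells the analyst to set a cut-off on every ROC. With 9.3 naming significant cancer as the key endpoint, one cut-off per modality is an equally natural reading, and on it pattern-3 sensitivity can fall far below 50%. That stands. The lower bound is conditional on the per-pattern reading, and what the text itself lacks is a statement of which reading applies.

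A reader might infer that the trial cannot show selectivity at all. The documents do not support this. Specificity and the ROC are primary beside sensitivity, and 9.7 adds that "we will use the bootstrapping method to detect the significant difference of the area under curve (AUC) with different ROC curves". The floor touches neither the curve nor the AUC. A pattern-3 sensitivity near 80% reported beside 30% specificity and an AUC of 0.50 would not mislead a careful reader.

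A reader might also blame the 50% floor for the whole effect. Step 3 shows otherwise: separate Youden cut-offs cause most of it, and deleting the floor alone is not a repair.

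For MRI, a reader might infer that the floor will usually force the cut-off that calls every sextant positive. If the lowest suspicious score truly flags 30% (40%) of 30 pattern-3 sextants, fewer than 15 are flagged with binomial probability 98% (82%). That leaves only the all-positive cut-off if no lower score is recorded, and the plan gives no score scale, so this is a possibility to close off and not a finding.

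Finally, 9.7 calls the pilot's data hypothesis generating, and no stopping or enrolment decision hangs on the pattern-3 cut-off. That lowers the severity. It does not remove the point, because 4.3 intends these figures to inform larger trials.

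**Conclusion.** The point holds, confined to the thresholded pattern-specific sensitivities. Section 9.7 leaves open which ROC sets the cut-off. Under a reading that it permits, pattern-3 sensitivity is at least 50% by construction and the patterns are judged at different cut-offs, so these sensitivities are not evidence for or against selectivity. With no pattern-3 signal, the choice of reading moves the reported figure from about 19–20% (8% in the SUV-based model) to about 80%.

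The bound itself rests on no assumption beyond the per-pattern reading. The sizes are illustrative: they assume the sextant mix, treat sextants as independent, and in the second model take lesion SUVs from a series of 10 high-risk patients. Severity: should-fix.

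**What to change.** In 9.7:

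1. Choose one cut-off per modality on the ROC for clinically significant cancer as 9.3 defines it (Gleason >6 and >5 mm), and state which sextants count as negative on that curve.
2. Apply that cut-off unchanged, and report the detection rate in pattern-3-only, pattern-4 and pattern-5 sextants.
3. Use the 50% floor only when choosing that one cut-off, not for pattern-specific results.
4. For MRI, state that the cut-off calling every sextant positive is not eligible. If no other score meets the floor, use the lowest score that the reader calls suspicious.
5. Keep the pattern-specific ROC and AUC as planned.

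The cost is wording only, with no new data or procedures, provided it is settled before the analysis. Reported pattern-3 sensitivities will be lower than under separate cut-offs.
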